9.4 STATISTICAL ANALYSES

Continuous data will be summarized with standard descriptive statistics (mean, standard deviation, median, minimum and maximum, 1st and 3rd quartiles). Categorical data will be summarized by frequencies and percentages.

No statistical test will be performed for between-group differences in demographic and baseline features (demographics and medical history).

Medical history and adverse events will be described according to System Organ Classes (SOC) and Preferred Terms (PT) using the Medical Dictionary for Regulatory Activities (MedDRA) and

will be presented by treatment group. Previous/concomitant medications will be presented by treatment group using the World Health Organization Drug Dictionary (WHO-DD).

All analyses will be performed using SAS® version 9.4

9.4.1 ANALYSIS OF VARIABLES

Phase II - Dose finding

Efficacy

The appropriate mannitol dose to be used in the comparative non-inferiority phase (phase III) will be singled out at the end of dose-finding based on the following criteria:

- 75% or greater rate of adequate bowel cleansing.
- Rate of patients in safe conditions, defined as the absence of potentially dangerous levels of H₂ and CH₄ in each colon segment (right, between ileocecal valve and appendix or as close as possible to the ileocecal valve in case of obstacles that prevent reaching the valve; transverse, including flexures; and left at the sigmoidal-rectum junction, 15-25 cm from anal margin) after standard washing and air insufflation for luminal distension).
- Clinical judgment based on the caecal intubation rate, the incidence of adverse events, treatment adherence and acceptability (considering ease of use, taste and willingness to reuse the preparation).

Should two or all three doses prove to be equally safe and effective, the lowest dose will be selected for phase III of the study.

Descriptive statistics and Wald 95% CI of the proportion of patients with adequate bowel cleansing will be provided for each dose.

In addition, a logistic regression model will be applied to assess the influence of the two stratification factors (constipation in the two weeks before the start of preparation for colonoscopy and centre) on dose response. A patient is considered a responder if he/she presents adequate bowel cleansing. In case of unbalanced enrolment among centres, a pooling approach will be adopted.

A supportive stepwise logistic regression model will also be applied to assess the influence on dose response of potential prognostic factors (i.e. age and previous unsuccessful bowel cleansing procedures) in addition to the two stratification factors. Based on the results from this model, the need to modify the stratification factors for phase III will be evaluated and the study protocol amended, if needed.

No between-group comparisons will be performed. The decision on the dose to be selected for phase III will be made on the basis of descriptive statistics and corresponding 95% CIs and on the

results of the logistic regression models. Endpoints will be analysed on the PP population. Results from the FAS will be used as supportive.

Caecal intubation rate

Descriptive statistics and Wald 95% CI of the caecal intubation rate will be provided for each dose.

Adherence and acceptability

Descriptive statistics and Wald 95% CIs of the following adherence and acceptability variables will be provided for each dose:

- Adherence
- NRS score for ease of use and taste
- Willingness to reuse the preparation

Phase II - Pharmacokinetic sub-study

The pharmacokinetic parameters (C_{max} , t_{max} , AUC_{0-t} , $t_{1/2}$) of each dose will be analysed descriptively on the PK population.

Phase III - Non-inferiority

Primary efficacy analysis

The proportion of patients with adequate bowel cleansing (BBPS total score ≥ 6 , score ≥ 2 for each segment) during colonoscopy after standard washing and air insufflation for luminal distension will be calculated to evaluate the non-inferiority of the test drug vs the standard drug.

Non-inferiority will be assessed by computing the two-tailed Wald 95% confidence interval (CI) of the difference between the two proportions $\pi_T - \pi_S$. Non-inferiority is met if the 95% CI does not cross the predefined non-inferiority margin $\Delta = -0.08$ and lies entirely to the right of the margin (i.e. non-inferiority will be demonstrated if the lower bound of the two-sided 95% CI of the difference is > -0.08).

The non-inferiority margin $\pi_T - \pi_S = -0.08$ corresponds to a relative risk $\pi_T/\pi_S = 0.906$ when the proportion of successes in the standard group is 0.85. Should the proportion of successes in the standard group be lower than 0.85, the non-inferiority margin will be adjusted in order to have a relative risk of at least 0.906 (e.g. if the proportion of successes observed in the standard group is 0.80, the non-inferiority margin $\pi_T - \pi_S$ will be set equal to $= -0.075$, corresponding to a relative risk equal to 0.906).

If the 95% CI of the difference lies completely to the right of 0, the test treatment can be considered superior to the standard treatment at a 5% significance level.

The Wald method for non-inferiority of proportions will be applied (*Dann RS, 2008*).

The analysis will be performed on both the FAS and PP populations. Results from both populations will have equal importance.

Secondary efficacy analyses

The analysis of secondary variables will be performed on the FAS. No between-group inferential analysis will be performed. Descriptive statistics and 95% CIs of the between-group differences will be applied on the following variables:

- Number, appearance, size, location and histological classification of neoplastic and inflammatory colorectal lesions detected
- Adenoma detection rate
- Caecal intubation rate
- Ottawa bowel preparation scale

Confidence intervals for proportions will be calculated based on the Wald method.

Adherence and acceptability

The analysis of adherence variables will be performed on the FAS. No between-group inferential analysis will be performed. Descriptive statistics and Wald 95% CIs of the between-group differences will be applied on the following variables:

- Bowel Cleansing Impact review (BOCLIR) scales
- Adherence
- NRS score for ease of use and taste
- Willingness to reuse the preparation

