
- T_0 (baseline before mannitol self-administration)
- T_1 (1 hour \pm 5 min after completion of mannitol self-administration)
- T_2 (2 hours \pm 5 min after completion of mannitol self-administration)
- T_4 (4 hours \pm 10 min after completion of mannitol self-administration, before colonoscopy)
- T_8 (8 hours \pm 10 min after completion of mannitol self-administration, after colonoscopy)

If patients do not undergo all PK evaluations, the sub-study sample size will be increased to guarantee at least 8 PK evaluations for each assessment time.

Phase III-Non-inferiority

A parallel-group design will be implemented to test the non-inferiority of bowel cleansing with the mannitol dose selected in phase II against standard split 2L PEG ASC. Phase III will begin only once all data collected from phase II necessary for establishing the optimal mannitol dose have been analysed. The non-inferiority study will involve 696 subjects randomized in a 1:1 ratio to one of the two cleansing agents. Randomization is stratified by centre.

Study visits

In both phases, the study will consist of four visits:

Visit 1 (\leq 28 days before the day of colonoscopy): after signed written informed consent is obtained from the patient, information concerning demographics, medical history, concomitant medications and indications for colonoscopy will be collected in the electronic case report form (eCRF).

Visit 2 (\leq 7 days before the day of colonoscopy): to complete the verification of inclusion/exclusion criteria, a blood sample will be drawn to assess the haematological and chemical parameters of all patients and to perform a pregnancy test for women of childbearing potential. Assessments include a urinalysis and the measurement of vital signs (heart rate and blood pressure).

Visit 3 (\leq 7 days before the day of colonoscopy): if eligibility criteria are met, the BSFS will be administered (only in phase II), randomization will be performed, study drug will be dispensed and verbal and written instructions for its use will be provided. Patients will be given a form on which to indicate date and time of start and end of study drug self-administration.

More than one visit may take place on the same day.

Visit 4 (day of colonoscopy):

- Phase II - dose finding

A blood and urine sample will be collected 4 hours \pm 30 minutes and 8 hours \pm 30 minutes after the end of study drug self-administration.

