4.1.1 PHASE II

The parallel-group dose-finding phase will be conducted at approximately 8 centres and will involve 150 patients randomly assigned (1:1:1 ratio) to one of the following three treatment groups:

- 50 g mannitol powder to be dissolved in 500 ml of water
- 100 g mannitol powder to be dissolved in 750 ml of water
- 150 g mannitol powder to be dissolved in 1000 ml of water

Of note, these doses of mannitol have been selected as this range includes the minimum (50 g) and maximum (150 g) mannitol doses used effectively in the proposed indication, as reported in published literature. Please refer to [Section 2.1](#) for further details.

Randomization is stratified by centre and by the presence of constipation (yes/no), defined as the recurrent use of laxatives or Bristol Stool Form Scale (BSFS) < 3 in the two weeks prior to randomisation.

To limit patient exposure to an ineffective dose causing repetition of colonoscopy, the adequacy of bowel cleansing will be monitored continuously and enrolment in a treatment group will be discontinued as soon as 25% of treated patients present inadequate bowel cleansing causing repetition of colonoscopy. The stopping rule, mainly guided by clinical considerations, will be applied in each treatment group as follows:

- Up to the 25th enrolled patient, enrolment in a treatment group will be stopped as soon as 6 patients present inadequate bowel cleansing causing repetition of colonoscopy (i.e. if among the initial 15 patients enrolled in a treatment group, 6 need to repeat the cleansing procedure, the treatment group will be immediately discontinued).
- From the 26th enrolled patient on (if treatment was not discontinued earlier), enrolment will be stopped as soon as 25% of patients present inadequate bowel cleansing causing repetition of colonoscopy (i.e. if among the initial 32 patients enrolled in a treatment group, 8 need to repeat the cleansing procedure, the treatment group will be immediately discontinued).

The appropriate mannitol dose to be used in the comparative non-inferiority phase (phase III) will be singled out at the end of dose-finding based on the following criteria:

- 75% or greater rate of adequate bowel cleansing.

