9 STATISTICAL CONSIDERATIONS

9.1 SAMPLE SIZE DETERMINATION

The total number of patients to be enrolled is approximately 846; 150 patients (50 in each mannitol dose group) for phase II dose finding, and 696 patients (348 in each treatment group) for the phase III non-inferiority study. The population for phase III will not include the patients who participated in phase II.

Phase II - Dose finding

The sample size is based on the precision of the estimate within each treatment group, i.e. the 95% confidence interval of the proportion of patients in each treatment group with adequate bowel cleansing (BBPS total score ≥ 6 , with BBPS ≥ 2 for each segment).

The table below shows the precision of the estimate for different rates of adequate bowel cleansing with a sample size of 50 patients.

Rates of adequate bowel cleansing (%)	Estimate Precision (%) (i.e. 95% CI*)
75	± 12
80	± 11
85	± 10

* Confidence interval estimated through normal approximation of binomial distribution without continuity correction.

Phase II - Pharmacokinetic sub-study

The expected sample size (10 patients in each dose group) is based on feasibility criteria.

Phase III - non-inferiority

The sample size is based on the proportion of patients with adequate bowel cleansing (BBPS total score ≥ 6 , with BBPS ≥ 2 for each segment). When the sample size in each group is 313, a two-group large-sample normal approximation test of difference of proportions with a one-sided 0.025 significance level will have 80% power to reject the null hypothesis that the test preparation is inferior to the standard preparation in favour of the alternative hypothesis that the test proportion is not inferior to the standard preparation (the difference in success proportions, $\pi_T - \pi_S$, is -0.08 or farther from zero in the same direction), assuming that the expected difference in success proportions is 0 and the proportion of successes in the standard group is 0.85 (the success rate for Moviprep® as reported in Bisschops R. et al., 2019, Choi et al., 2018 and Kwon et al., 2016 varies from 85% to 89%).

A proportion of patients with adequate bowel cleansing 8% lower than the expected 85% for gold standard Moviprep® would give a 77% success rate for mannitol, which falls within the 70-88.5% range reported for PEG-ASC (Repici et al., 2012; Choi et al., 2018; Hassan et al., 2013).

Sample size for two-group test of equivalence in proportions (large equal n's)

Test significance level, α (one-sided)	0.025

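### Stepwise selection over four named factors in at most 150 phase II patients is an unreliable basis for reviewing the phase III strata, and the plan is inconsistent on whether the logistic models inform the dose choice

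*Combined protocol and SAP*

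**What the plan says.** Section 9.4.1 (Phase II - Dose finding, Efficacy) plans two logistic analyses of adequate cleansing.

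- The first assesses the two stratification factors, constipation and centre, with pooling of centres if enrolment is unbalanced. It is not described as stepwise.
- The second reads: "A supportive stepwise logistic regression model will also be applied to assess the influence on dose response of potential prognostic factors", the factors being "i.e. age and previous unsuccessful bowel cleansing procedures) in addition to the two stratification factors". No entry level, stay level or list of forced terms follows.

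On use of the second model, the section says: "Based on the results from this model, the need to modify the stratification factors for phase III will be evaluated", with a protocol amendment if needed. It then bases the dose decision on descriptive statistics, 95% CIs and the "results of the logistic regression models". The synopsis (Section 1.1, Analysis of primary variables) mentions logistic models but rests the dose decision on descriptive statistics and 95% CIs only.

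Section 9.1 gives the size: "150 patients (50 in each mannitol dose group) for phase II dose finding". It also gives the rationale: "The sample size is based on the precision of the estimate within each treatment group". Phase II endpoints are analysed on the PP population with the FAS as support, so 150 is the upper limit for the model.

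**The concern.** Variable selection earns its place when there are many candidates and little prior knowledge. Here four factors are named in advance, so nothing needs to be selected. In a sample of this size, whether a factor is retained depends heavily on chance and on an entry level that the plan leaves open. Two errors follow. A factor that matters can go missing from the final model and be taken as unimportant. A factor that is retained carries an odds ratio too far from 1, because it had to look large to get in.

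Phase III is at present stratified by centre only. The practical risk is therefore failing to add a useful stratum, or adding one on an inflated estimate. The unsettled role of the models in the dose decision is a second, separate matter: a reader cannot tell whether their output counts.

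**Working it through.** **1. The plan's own phase II figure.** Section 9.1 gives precision for one proportion with n = 50: 1.96 × √(p(1−p)/50). At p = 0.75, 0.80 and 0.85 this is 12.0, 11.1 and 9.9 points, matching the stated ±12, ±11 and ±10. Phase II was sized for one rate per dose, not for covariate effects.

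**2. Precision for a covariate in 150 patients.** Take 80% success without the factor and 65% with it (a 15-point effect; an assumption). With n₁ = 150 × prevalence and n₀ = 150 − n₁, the half-width is 1.96 × √(0.65×0.35/n₁ + 0.80×0.20/n₀).

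| Prevalence | n₁ / n₀ | 95% CI half-width (points) |
|---|---|---|
| 10% | 15 / 135 | 25.1 |
| 15% | 22.5 / 127.5 | 20.9 |
| 20% | 30 / 120 | 18.5 |
| 30% | 45 / 105 | 15.9 |
| 50% | 75 / 75 | 14.1 |

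With half-widths near or above 15 points, a true 15-point effect will often miss a 0.05 criterion.

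**3. Retention under selection (simulation).** Assumptions not in the documents: 150 patients, dose forced in, 80% or 85% success without the factor, a true 15-point deficit with it, entry level 0.05 or 0.15. The true odds ratios are (0.65/0.35)/(0.80/0.20) = 0.46 and (0.70/0.30)/(0.85/0.15) = 0.41.

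| Factor | Retained, level 0.05 | Retained, level 0.15 |
|---|---|---|
| Previous unsuccessful cleansing, 10-15% prevalence, constipation forced in | 23-37% | 43-55% |
| Constipation, 20-30% prevalence, as a candidate | 39-53% | 59-72% |

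When previous unsuccessful cleansing is retained, its median odds ratio is 0.22-0.29 at level 0.05 and 0.27-0.34 at level 0.15. The full model gives 0.42-0.48. For constipation as a candidate at level 0.05, the median when retained is 0.28-0.35 against a true 0.41-0.46.

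**4. Sensitivity to the unstated rule.** A wider run used constipation prevalence 15-50%, five pooled centre groups, a score test to enter and a Wald test to stay. Constipation as a candidate was dropped in 43-64% of trials at level 0.05 and 21-49% at level 0.15. At least one of two factors with no true effect entered in 7-10% and 20-27% of trials respectively. With 135 patients the dropped share reached 69% at level 0.05 (some high-prevalence settings were not run at that size).

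**5. Number of terms.** Dose (2), constipation, age, previous unsuccessful cleansing and 12 centre terms (13 sites in the synopsis) make 17. At 80% success there are 150 × 0.20 = 30 failures, or 30/17 = 1.8 per term; at 75% there are 37.5, or 2.2. With the 8 centres of Section 4.1.1 there are 5 + 7 = 12 terms and 30/12 = 2.5. Centre therefore needs pooling or a random effect in any model.

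**6. The dose decision.** Section 9.4.1 lists descriptive statistics, 95% CIs and the logistic models. Section 1.1 lists descriptive statistics and 95% CIs. Both are current text, and both cannot be the complete basis.

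**The case against.** The strongest reply is that little hangs on this model. It is labelled supportive. It prompts an evaluation, with any change going through an amendment, and no rule says that a factor not retained will be ignored. That stands: a reader might infer that the stepwise result decides the phase III design, and the text does not say so.

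A reader might also infer that constipation would be lost about half the time. That does not hold as a general statement. Constipation and centre are estimated in the separate model whatever the stepwise run does. The phrase placing the new factors alongside the stratification factors can also be read as forcing those in, in which case constipation is never dropped. Prevalence, effect size, baseline rate and entry level are all assumed, and the dropped share runs from about 21% to 69% across the ranges tried. What survives is that age and previous unsuccessful cleansing are selected under either reading. The first row of the retention table shows the problem for previous unsuccessful cleansing under the reading kinder to the plan.

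Third, a full model creates no power. That is true, as the half-widths show. It does report the uncertainty, instead of turning it into a retained or not-retained label.

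Finally, the consequences for phase III are limited. Its primary analysis is an unadjusted Wald interval, no covariate or subgroup use of constipation is planned, and the synopsis already says of the stool scale: "the BSFS will be administered (only in phase II" (Section 1.1, Visit 3). The stepwise result takes nothing away there.

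**Conclusion.** The point holds as a minor one. Selection over four prenamed factors, with no stated rule, is a weak basis for reviewing the phase III strata, and a better method costs nothing. For a true 15-point effect, previous unsuccessful cleansing would be retained in about 23-55% of trials. Constipation would be retained in about 39-72%, but only if it is a selection candidate. Retained odds ratios are exaggerated in both cases. These figures rest on the assumed prevalences, success rates and entry levels above. No effect of age was simulated; the argument for age is by analogy.

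Two further inferences are not supported. One is that a wrong dose would follow: the stated criteria are the 75% adequacy rate, gas safety and clinical judgment, and no rate of wrong dose choice has been calculated. The other is that the missing stool scale in phase III is a harm of the stepwise model: it matters only if constipation is later used there. The disagreement between Sections 1.1 and 9.4.1 on the dose decision is a matter of text and needs no assumption.

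**What to change.** In Section 9.4.1, replace the stepwise model with one prespecified logistic model containing dose, constipation as randomised, age, previous unsuccessful cleansing, and centre either pooled into few groups or as a random effect. Report odds ratios with 95% CIs. State that any change to the phase III strata will be judged on those estimates and intervals, not on whether a variable was retained. Reconcile Sections 1.1 and 9.4.1 on whether the logistic models inform the dose decision. Using constipation as randomised also settles its time window, which Section 9.2 counts back from randomisation and Section 9.4.1 from the start of preparation.

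Cost: wording only, with no new data and less programming than a selection procedure. The limitation is that intervals stay wide: about ±14 to 19 points for constipation at 20-50% prevalence, and wider for a rarer factor. Collecting the stool scale in phase III would be needed only if constipation may be used there, and is not part of this change.

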Study Endpoints	
Phase II - Dose finding
 
● Primary efficacy endpoint: proportion of patients with adequate bowel cleansing, defined as Boston Bowel Preparation Scale (BBPS) total score ≥ 6, with a score for each of the three colon segments (right; transverse, including flexures; and left, including sigmoid and rectum) ≥ 2 during colonoscopy after standard washing and air insufflation for luminal distension.● Secondary efficacy endpoint: caecal intubation rate, defined as the percentage of patients with appendiceal orifice visible to the endoscopist.● Safety and tolerability
○ Proportion of patients in safe conditions, defined as the absence in each colon segment (right, between ileocecal valve and appendix or as close as possible to the ileocecal valve in case of obstacles that prevent reaching the valve; transverse, including flexures; and left at the sigmoidal-rectum junction, 15-25 cm from anal margin) of potentially dangerous levels of H_2 and/or CH_4 ($>4\% Vol$ and $>100\% of Lower Explosion Level (LEL)$, which is equal to 5% Vol, respectively) during colonoscopy after standard washing and air insufflation for luminal distension.○ Incidence of adverse events from the beginning of study drug self-administration.○ Proportion of patients with change from baseline considered clinically significant by the Investigator of haematological and chemical parameters (CBC, creatinine, BUN, eGFR, ALT, AST, glucose, electrolytes) 4 hours and 8 hours after completion of study drug self-administration.○ Proportion of patients with change during colonoscopy considered clinically significant by the Investigator of vital signs (heart rate and pulse oximetry).

	
Of note, a clinically significant change of a given parameter is defined as a change that causes an additional control or a medical intervention.
 
• Adherence and acceptability
◦ Adherence: study drug completely taken, partially taken, not taken.◦ Ease of use: numeric rating scale (NRS) (0=very difficult to 10=very easy).◦ Taste: NRS (0=terrible to 10=very good).◦ Willingness to reuse the preparation (yes/no).

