9.3 POPULATIONS FOR ANALYSES

The following populations will be used for the statistical analyses:

- Safety set: all patients who take the study preparation, even only partially. Patients will be analysed according to the study drug dose actually received.
- Modified Safety set: all patients who take the study preparation, even only partially, and who do not meet significant protocol violations that regard inclusion/exclusion criteria. Patients will be analysed according to the study drug dose actually received.
- PK population (only for the pharmacokinetic sub-study): all randomized patients who complete the mannitol treatment and have at least one PK assessment, regardless of the outcome of colonoscopy. Patients will be analysed according to the study drug dose actually received.
- Full Analysis Set (FAS): all randomized patients who take the study preparation, even only partially, undergo the colonoscopy, and have a BBPS available for at least one colon segment after standard washing and air insufflation for luminal distension. According to the Intention to Treat (ITT) principle, patients will be analysed according to the study drug dose assigned at randomization.
- Per protocol (PP): all randomized patients who meet the following criteria:
 - Treatment with the study drug completed.
 - Colonoscopy completed adequately in absence of pathological obstruction that prevents reaching the right colon, including the cecum (i.e. endoscope does not find obstacles other than faecal material) and without acute deterioration of general conditions causing procedure suspension.
 - Bowel cleansing assessment and gas measurement are available for all colon segments after standard washing and air insufflation for luminal distension.
 - No significant protocol violations that regard inclusion/exclusion criteria or that can condition evaluations.

Patients will be analysed according to the study drug dose actually received.

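### The phase II caecal intubation rate is read mainly on the per-protocol set, which drops patients whose right colon was not reached instead of counting them as failures; the FAS should be the main set, as in phase III

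*Combined protocol and SAP*

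**What the plan says.** The Synopsis lists a single secondary efficacy endpoint for phase II: "Secondary efficacy endpoint: caecal intubation rate, defined as the percentage of patients with appendiceal orifice visible to the endoscopist". Section 9.4.1 makes it part of the third dose-selection criterion: "Clinical judgment based on the caecal intubation rate, the incidence of adverse events, treatment adherence and acceptability". No numerical threshold is attached to it.

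On the analysis set, the phase II efficacy text in Section 9.4.1 says "Endpoints will be analysed on the PP population" and then "Results from the FAS will be used as supportive". The short paragraph on caecal intubation that follows asks for descriptive statistics and a Wald interval per dose and names no other set.

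Section 9.3 defines PP. Two of its conditions matter here: "Colonoscopy completed adequately in absence of pathological obstruction that prevents reaching the right colon, including the cecum", and "Bowel cleansing assessment and gas measurement are available for all colon segments". The FAS needs only some intake of the preparation, a colonoscopy, and a Boston scale (BBPS) score in at least one segment.

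For phase III, where caecal intubation is again a secondary efficacy endpoint, Section 9.4.1 says "The analysis of secondary variables will be performed on the FAS".

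**The concern.** Entry to PP depends on how far the colonoscope went, and that is largely what the caecal intubation rate measures. If the scope stops in the transverse colon, there is no right-segment score and no right-segment gas reading. The patient then leaves the denominator and is not counted as a failure. The error runs in one direction, so the rate looks better than it was.

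This matters because the rate feeds the choice of the phase III dose, and Section 4.1.1 sends the lowest dose forward when doses are judged equally safe and effective. An analysis that tends to shrink dose differences makes that judgement easier to reach. Phase III already puts the same endpoint on the FAS, and the protocol gives no reason for treating phase II differently.

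**Working it through.** **The plan's own figure.** The documents give no expected caecal intubation rate. The only phase II precision figures are those in Section 9.1 for adequate cleansing with 50 patients per dose. The formula 1.96·√(p(1−p)/50) gives 12.0, 11.1 and 9.9 points at 75%, 80% and 85%, which matches the stated ±12, ±11 and ±10.

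**Which failures stay in PP.**
- Right colon not reached, for any reason: no right-segment readings, so the all-segments condition excludes the patient.
- Pathological obstruction before the right colon or caecum, or a procedure suspended for acute deterioration: excluded by the completion condition.
- Right colon scored and sampled, but appendiceal orifice not seen: can stay in PP as a failure. Section 9.3 does not treat stool as an excluding obstruction, and Section 8.1.1 lets the right-segment gas sample be taken short of the valve if the valve cannot be reached.

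**Formula.** Let c be the intubation rate before exclusion and f the share of failures that PP removes, with successes assumed kept. Then PP rate = c / (c + (1−c)(1−f)). The documents do not give f, so its range is 0 to 1.

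**Scenario A: failure rates cited in Section 2.1.** One PEG trial reports failed intubation of 11.7% with fair/poor and 1.2% with good/excellent preparation. For an assumed adequate-cleansing rate a, the failure rate is (1−a)·0.117 + a·0.012.

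| a (assumed) | Failure rate | Failures per 50 | Rate, f=0 | Rate, f=0.5 | Rate, f=1 |
|---|---|---|---|---|---|
| 60% | 5.4% | 2.7 | 94.6% | 97.2% | 100% |
| 75% | 3.8% | 1.9 | 96.2% | 98.1% | 100% |
| 85% | 2.8% | 1.4 | 97.2% | 98.6% | 100% |

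The distortion is at most 100 − 94.6 = 5.4 points. The spread from lowest to highest is 2.6 points with nothing removed, 1.4 points at f=0.5 and 0 at f=1. For scale, the Wald half-width at n=50 is 1.96·√(0.946·0.054/50) = 6.3 points at 94.6%, and 1.96·√(0.972·0.028/50) = 4.6 points at 97.2%.

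**Scenario B: more frequent failure.** Section 2.1 also cites incomplete colonoscopy in 10% to 20% of examinations, under a broader definition that includes poor mucosal visualisation. Take true rates of 85% and 95% at two doses as an illustration.

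| f | Dose with 85% | Dose with 95% | Gap (points) |
|---|---|---|---|
| 0 | 85.0% | 95.0% | 10.0 |
| 0.25 | 88.3% | 96.2% | 7.9 |
| 0.5 | 91.9% | 97.4% | 5.5 |
| 0.75 | 95.8% | 98.7% | 2.9 |
| 0.9 | 98.3% | 99.5% | 1.2 |
| 1 | 100% | 100% | 0 |

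**Dependence on a common f.** The upward bias at each dose needs only f above 0. The compression of the gap needs f to be similar across doses, or higher at the worse dose. With f=0.25 at the worse dose and 0.75 at the better one, the gap is 98.7 − 88.3 = 10.4 points, so it is not compressed.

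**The case against.** The case for leaving the text alone has four parts.

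1. *The FAS rate is already planned.* This stands. Patients removed from PP would show in the contrast between the two tables. A reader might infer that the phase II and phase III rates cannot be compared, but the documents do not support that: the supportive phase II FAS rate can be set beside the phase III FAS rate. What remains is that the biased figure leads, and no rule says what happens if the two sets disagree.

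2. *Not all failures are removed.* This also stands. The treatment of stool and the flexible right-segment gas site keep some failures in PP. A reader might infer that PP removes every failure, or some fixed majority of them, but no document gives the share. The stool clause helps only under the obstruction condition, however. A stool-blocked patient with no right-segment readings is still excluded by the all-segments condition.

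3. *The doses may look alike anyway.* A reader might infer that PP is what makes the doses look alike near 100%. On the cited failure rates they would lie at about 95% to 97% before any exclusion, within sampling error of one another at 50 per dose. PP adds to this but does not create it.

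4. *The effect on dose choice is limited.* The rate is one of several judgement inputs. The numerical efficacy criterion is adequate cleansing of at least 75%, and the 25% stopping rule in Section 4.1.1 works on treated patients, not on PP. This limits the priority of the point but does not justify conditioning an endpoint on its own outcome.

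It could also be argued that the PP sentence covers only the primary endpoint. It is plural and stands under efficacy. If the narrower reading is meant, the set for caecal intubation is unspecified and the same edit is needed.

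**Conclusion.** The point holds with a limited size. PP as main set biases the phase II caecal intubation rate upward at any dose where failures are removed. It also compresses dose differences if the share removed is similar across doses or higher where cleansing is worse.

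On the failure rates cited in Section 2.1 and assumed adequacy of 60% to 85%, the distortion runs from 0 to about 5 points. If true failure were 15% against 5%, a 10-point gap would read as 5.5 points with half of failures removed and 0 with all removed.

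These figures rest on three assumptions: the share removed is unknown, successes are kept in PP, and the cited rates come from a PEG trial with a different quality grading, not from mannitol or the BBPS. The documents show no route by which this alone would lead to a different dose being chosen. It is worth correcting because the bias has a known direction and the correction is simple.

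**What to change.** In Section 9.4.1, phase II, under caecal intubation rate:

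- State that the FAS is the main analysis set, as it already is for phase III, and that PP is supportive.
- Count non-visualisation of the appendiceal orifice for any reason as a failure.
- State that this FAS rate is the one used in dose selection.
- Add a table by dose of the reasons for non-visualisation (stool, pathological obstruction, intolerance, other), so that failures unrelated to the preparation can be told apart.

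The cost is a few sentences and one table. No new data are needed and the sample size does not change. The reported phase II rates become slightly less favourable and will include some failures, such as those from pathological obstruction, that no preparation could have prevented. A small gap remains: a patient with no segment scored is outside the FAS too, and should be listed separately by dose.
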